## 12.5 Analysis Populations

The populations for analysis will include the intent-to-treat (ITT), intent-to-treat infected (ITTI and ITTI-A), per-protocol infected (PPI), and safety populations. Additional analysis populations may be defined to evaluate study results. Any additional analysis populations will be defined in the SAP.

**Intent-To-Treat Population:** The ITT population will include all subjects who are randomized. Subjects will be analyzed in the treatment group to which they were randomized. The ITT population will be used for analyses of accountability and demographics.

**Intent-To-Treat Infected Population:** The ITTI population will include all subjects who are randomized, received study drug, and have confirmed influenza by culture or PCR. Subjects will be analyzed according to the treatment randomized. If a discrepancy is noted in the final database for any subject, such that the drug differs from the randomized treatment assignment, efficacy analyses may be repeated with the subjects analyzed according to the treatment received. The ITTI population will be used for primary analyses of efficacy.

**Intent-To-Treat Infected Population-A:** The ITTI-A population will include all subjects who

are randomized, received study drug, and have confirmed influenza A by culture or PCR. Subjects will be analyzed according to the treatment randomized. If a discrepancy is noted in the final database for any subject, such that the drug differs from the randomized treatment assignment, efficacy analyses may be repeated with the subjects analyzed according to the treatment received. The ITTI-A population will be used for supportive analyses of efficacy.

**Per-Protocol Infected:** The PPI population includes all subjects in the ITTI population who receive an adequate intramuscular injection. The definition of an adequate intramuscular injection will be further described in the SAP. The PPI population will be used for supportive analyses of efficacy.

**Safety Population:** The safety population will include all subjects who received study drug. Subjects will be analyzed according to the treatment received. This population will be used for all safety analyses.

## 12.6 Interim and End of Study Analyses

### Interim Analysis

An independent DMC will review safety data on an ongoing basis. Safety analyses will be presented in a manner consistent with the presentations intended for the final analysis.

### End of Study Analysis

A final analysis is planned after the last subject completes or discontinues the study, and the resulting clinical database has been cleaned, quality checked, and locked.

## 12.7 Efficacy Analyses

### 12.7.1 Primary Efficacy Endpoint

The primary efficacy endpoint is the time to alleviation of symptoms of influenza in subjects diagnosed with influenza, defined as the time from injection of study drug to the start of the time period when a subject has Alleviation of Symptoms. A subject has Alleviation of Symptoms if all of the seven symptoms of influenza (nasal congestion, sore throat, cough, aches and pains, fatigue (tiredness), headache, feeling feverish) assessed on his/her subject diary are either absent or are present at no more than mild severity level and at this status for at least 21.5 hours (24 hours - 10%).

Descriptive statistics for the primary efficacy variable will be tabulated by treatment group. Alleviation of symptoms will be determined by assessment of symptoms as reported on each subject's diary card. Time to alleviation of symptoms will be summarized for each treatment group (300 mg peramivir and placebo). Treatment comparisons between the 300 mg peramivir group and placebo will be assessed using a Wilcoxon-Gehan statistic stratified by smoking status and positive PCR or viral culture for influenza A or B at screening for the ITTI and PPI populations. Subjects who do not experience alleviation of symptoms will be censored at the date of their last non-missing post-baseline assessment.

### 12.7.2 Secondary Efficacy Endpoints

All secondary endpoints will be summarized using descriptive statistics by treatment group, and study day/time, if appropriate. Statistical comparisons for each endpoint will be constructed without adjustment for multiple endpoints.

The reduction in viral shedding will be assessed as the change in viral titers defined as the time-weighted change from baseline in  $\log_{10}$  tissue culture infective dose50 (TCID50/mL) and will be summarized for each treatment group. The time-weighted average change from baseline will be calculated on a by-subject basis through Day 9 using the trapezoidal rule with all available data (data after initiation of study treatment) minus the baseline value. Specifically, the time-weighted area under the curve for time a ( $t_a$ ) to time b ( $t_b$ ) is given by the formula

$$TWAUC = \frac{AUC(t_a - t_b)}{(t_a - t_b)},$$

where  $AUC(t_a - t_b) = \sum_{i=a}^{b-1} \frac{(y_i + y_{i+1})(t_{i+1} - t_i)}{2}$  and  $t_i$  represents the date of the  $i^{\text{th}}$  viral titer

assessment and  $y_i$  represents the  $\log_{10}$  value of the  $i^{\text{th}}$  viral titer assessment. If there is a baseline value and only one follow-up value,  $y_i$  then the time-weighted change from baseline is defined as the difference between  $y_i$  and baseline. If there is a baseline value and no follow-up value, the subject is excluded from analysis. The differences between the 300 mg peramivir treatment group and placebo will be evaluated using a van Elteren Test adjusting for smoking status and positive PCR or viral culture for influenza A or B at screening.

Subject's oral temperature will be summarized by study visit and treatment group. Differences between the 300 mg peramivir treatment group and placebo will be assessed using the van Elteren test controlling for smoking status and positive PCR or viral culture for influenza A or B at screening. A subject has Resolution of Fever if he/she has a temperature  $< 37.2^{\circ}\text{C}$  ( $99.0^{\circ}\text{F}$ ) and no antipyretic medications have been taken for at least 12 hours. The time to resolution of fever will be estimated using the method of Kaplan-Meier using temperature and symptom relief medication information obtained from the subject diary data. Differences between the treatment groups will be assessed using the Wilcoxon-Gehan statistic controlling for smoking status and positive PCR or viral culture for influenza A or B at screening. Subjects who do not have resolution of fever will be censored at the time of their last non-missing post-baseline temperature assessment.

The number and percentage of subjects experiencing influenza related complications will be summarized by complication preferred term and treatment group. The difference between the treatment groups (300 mg peramivir and placebo) will be assessed using a Cochran-Mantel-Haenszel (CMH) test statistic controlling for smoking status, and positive PCR or viral culture for influenza A or B at screening, if applicable.

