### 12.7.2 Secondary Efficacy Endpoints

All secondary endpoints will be summarized using descriptive statistics by treatment group, and study day/time, if appropriate. Statistical comparisons for each endpoint will be constructed without adjustment for multiple endpoints.

The reduction in viral shedding will be assessed as the change in viral titers defined as the time-weighted change from baseline in  $\log_{10}$  tissue culture infective dose50 (TCID50/mL) and will be summarized for each treatment group. The time-weighted average change from baseline will be calculated on a by-subject basis through Day 9 using the trapezoidal rule with all available post-baseline on-treatment data (data after initiation of study treatment) minus the baseline value. Specifically, the time-weighted area under the curve for time a ( $t_a$ ) to time b ( $t_b$ ) is given by the formula

$$TWAUC = \frac{AUC(t_a - t_b)}{(t_a - t_b)},$$

where  $AUC(t_a - t_b) = \sum_{i=a}^{b-1} \frac{(y_i + y_{i+1})(t_{i+1} - t_i)}{2}$  and  $t_i$  represents the date of the  $i^{\text{th}}$  viral titer

assessment and  $y_i$  represents the  $\log_{10}$  value of the  $i^{\text{th}}$  viral titer assessment. If there is a baseline value and only one follow-up value,  $y_i$  then the time-weighted change from baseline is defined as the difference between  $y_i$  and baseline. If there is a baseline value and no follow-up value, the subject is excluded from analysis. The differences between each of the peramivir treatment groups and placebo will be evaluated using a van Elteren Test adjusting for smoking status at screening. Analyses of the PCR results will be analyzed in a similar manner.

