#### 6.2.2 Secondary Endpoint(s)

Secondary safety, clinical, and virologic endpoints will include evaluations in each subject of:

Safety: Incidence of treatment-emergent adverse events and treatment-emergent changes in clinical laboratory tests.

Clinical: Time to resolution of fever; Incidence of influenza related complications.

Virologic: Quantitative change in influenza virus shedding, measured by viral titer assay (TCID50).

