Anterior nose (bilateral) and posterior pharynx specimens (swabs) will be collected at Day 1 (pre-treatment) and at Days 3, 5, and 9, for quantitative virologic assessments. Specimens from all subjects yielding influenza virus will also be assessed for susceptibility to neuraminidase inhibitors (Day 1 and last specimen yielding positive result) as well as other virologic

assessments (e.g. PCR, genotypic testing). All virologic assessments will be performed by a central laboratory.

Two samples for pharmacokinetic (PK) testing for plasma levels of peramivir will be obtained from all subjects randomized. The first PK sample will be obtained between 30 and 60 minutes following study drug administration in all subjects. The second PK sample will be obtained at the day 3 visit in all subjects. The data from these PK samples will be utilized in a population exposure-response analysis.

At selected sites a separate sub-study will be conducted to collect additional PK samples between treatment and Day 3 for the purpose of conducting a separate exposure-response analysis. This sub-study will be conducted under a separate protocol, BCX1812-311PK.

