### **12.10.2 Covariates**

Primary and secondary efficacy analyses will be adjusted for smoking status and positive PCR or viral culture for influenza A or B at screening, where appropriate.

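### The printed viral titre formula divides by a negative interval, so taken literally it does not give the change from baseline; correct the sign and name the swab at which the area starts

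*Combined protocol and SAP*

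**What the plan says.** Section 6.2.2 of protocol Version 4.0 lists one virologic secondary endpoint: "Quantitative change in influenza virus shedding, measured by viral titer assay" (TCID50). Shedding by PCR is exploratory (Section 6.2.3). Swabs "will be collected at Day 1 (pre-treatment) and at Days 3, 5, and 9, for quantitative virologic assessments" (Section 7.1).

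Section 12.7.2 turns the titres into one score per subject, through Day 9, "using the trapezoidal rule with all available data (data after initiation of study treatment) minus the baseline value". The formula is printed as "TWAUC = \frac{AUC(t_a - t_b)}{(t_a - t_b", with the brackets then closed. The area is the sum, for i from a to b − 1, of (y_i + y_{i+1})(t_{i+1} − t_i)/2. No visit is assigned to `t_a`. If a subject has a baseline and a single follow-up value, "then the time-weighted change from baseline is defined as the difference between" that value and baseline.

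The arms are compared by a rank test: the difference "will be evaluated using a van Elteren Test adjusting for smoking status and positive PCR or viral culture for influenza A or B" at screening. Section 12.10.2 names the same two factors. Section 12.2 leaves further technical detail to an SAP; the combined file holds five protocol texts but no SAP text.

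**The concern.** The area is accumulated forward in time, so `t_a` precedes `t_b` and the printed divisor is negative. Because baseline is subtracted after the division, the slip does more than change the sign of the final score. It produces a different variable, one in which a high post-treatment titre looks like a large reduction. A rank test on that variable would rank subjects wrongly and would tend to show any treatment effect in the opposite direction.

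The same paragraph never ties `t_a` to a swab. The wording favours the first post-treatment swab, but a programmer who started at the Day 1 swab would obtain different scores. Both matters lie in the text that defines the endpoint, so they are best settled before programming.

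**Working it through.** The documents give no sample size, power or effect size for the titre endpoint, so there is no planned figure to reproduce. The inputs are the formula and the one-follow-up rule (Section 12.7.2) and the nominal swab days 1, 3, 5 and 9 (Section 7.1). All titres below are invented for illustration.

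**Sign.** Let M be the true time-weighted average, area/(`t_b` − `t_a`), and y_0 the baseline.

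- Intended score: M − y_0.
- Printed score: area/(`t_a` − `t_b`) − y_0 = −M − y_0 = −(M + y_0).
- Randomisation makes y_0 equal between arms in expectation, so the expected arm difference in the printed score is minus the difference in M: the direction is reversed.

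Two subjects with baseline 5.0, area from Day 3:

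| Subject | Days 3/5/9 | Area | As printed | As intended |
|---|---|---|---|---|
| A | 4.0/2.0/0.5 | (4+2)×2/2 + (2+0.5)×4/2 = 11.0 | 11/(3−9) − 5 = −6.83 | 11/(9−3) − 5 = −3.17 |
| B | 1.0/0.5/0.5 | (1+0.5)×2/2 + (0.5+0.5)×4/2 = 3.5 | 3.5/(−6) − 5 = −5.58 | 3.5/6 − 5 = −4.42 |

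B cleared virus faster and should rank as the larger reduction; as printed, A does. A flat profile of 3, 3, 3, 3 should score 0: area 18, 18/6 − 3 = 0. As printed it scores −18/6 − 3 = −6, whereas a subject with baseline 3 and one follow-up value of 3 scores 3 − 3 = 0 by the stated rule. The printed formula therefore disagrees with the section's own rule.

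**Start of the area, sign corrected.** Three features of Section 12.7.2 favour a post-treatment start: the data are those after treatment begins, while the Day 1 swab is taken before it; baseline is subtracted separately; and the one-follow-up rule fits only that start. For one follow-up y_1:

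- From a post-treatment start, the formula is 0/0 and the rule fills the gap with y_1 − y_0.
- From baseline, the formula gives (y_0 + y_1)/2 − y_0 = (y_1 − y_0)/2, half of what the rule gives.

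The superseded Version 3.0 wording, "on-treatment data (data after initiation of study treatment) minus the baseline value", points the same way and is cited only for intent. If Day 1 were used despite this, a constant drop d would score (2d+3d+2d)/8 = 0.875d with all three swabs and (2d+d)/4 = 0.75d with Days 3 and 5 only. From Day 3 it scores d in both cases. Subject A would move from −3.17 to (9+11)/8 − 5 = −2.50, passing a subject with baseline 5.0 and only a Day 3 value of 2.0, who scores −3.00 by the rule.

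**Scale of the sign error, by simulation.** Assumptions: 300 against 150 subjects; baseline mean 4 and SD 1.0 to 1.5; residual SD 1.2 per swab; slope of follow-up on baseline 0.3 to 0.5; effects of 0.3 log10 at each swab, or 0.5/0.3/0.05 at Days 3/5/9; unstratified Wilcoxon test in place of van Elteren; area from Day 3. The Spearman correlation between printed and intended scores was about 0.1 to 0.5. The rejection rate fell from 0.61–0.91 to 0.18–0.42. The mean difference changed sign (−0.30 became about +0.29 to +0.30 in the constant-effect cases), so those remaining rejections would mostly favour placebo.

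**The case against.** The strongest reply on the sign is that this is notation. In the numerator, AUC(`t_a` − `t_b`) can only label the range from `t_a` to `t_b`; read alike, the denominator is the length of that range. The words around it describe an average change from baseline, and routine checking should catch a negative mean titre. This stands as to intent. It does not make the printed quotient right: in a denominator those symbols are a subtraction. The same divisor is printed in all five protocol texts, so it is not a fault of PDF extraction.

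A reader might infer that the plan leaves the start of the area open. The documents do not support that. Section 12.7.2 favours a post-treatment start, and the 0.875d and 0.75d factors and the rank exchange all arise only under the disfavoured Day 1 reading. What remains is that no visit is named.

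A reader might also infer that a test without baseline titre as a covariate is biased. It is not: treatment is randomised, and the stratified van Elteren test on the change score is valid. A baseline covariate is a question of efficiency. Its gain cannot be sized, because the documents give no titre SD or correlation.

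Finally, the SAP may already settle the first two matters. That stands; if it does, only the protocol text needs correcting.

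**Conclusion.** The printed formula is wrong as written. Its divisor is negative, and the resulting score, −(average + baseline), ranks subjects differently from the change that the text describes. The algebra needs only that `t_a` precede `t_b`; the sizes shown rest on invented titres and assumed variances. It is most likely a slip whose intent can be recovered, and nothing in the documents shows that any result will be computed from the literal formula. `t_a` needs naming, not choosing afresh. The point concerns one secondary endpoint; the primary analysis is unaffected. It should be corrected, at very small cost.

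**What to change.** - In Section 12.7.2, print the divisor as (`t_b` − `t_a`), and use the same form in the SAP.
- In the same sentence, state that `t_a` is the first post-treatment swab. The one-follow-up rule then stands unchanged.
- Optionally, prespecify a supportive stratified rank ANCOVA of the time-weighted average log10 titre on baseline log10 titre, with the same strata, beside the van Elteren test and not in its place.

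The cost of the first two is one symbol and one clause. No new visit or sample is needed: the pre-dose swab is already scheduled (Section 10.3.1), and the change score already requires a baseline titre.

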## 8 SELECTION AND WITHDRAWAL OF SUBJECTS

### 8.1.1 Inclusion Criteria

Subjects must meet all of the following criteria for inclusion in this study:

1. Male and non-pregnant female subjects age  $\geq 18$  years.
2. A positive Influenza A and/or B Rapid Antigen Test (RAT) performed with a commercially available test kit on an adequate anterior nasal specimen, in accordance with the manufacturer's instructions. A negative initial RAT should be repeated within one hour.
3. Presence of fever at time of screening of  $\geq 38.0$  °C ( $\geq 100.4$  °F) taken orally, or  $\geq 38.5$  °C ( $\geq 101.2$  °F) taken rectally. A subject self-report of a history of fever or feverishness within the 24 hours prior to screening will also qualify for enrollment in the absence of documented fever at the time of screening.
4. Presence of at least one respiratory symptom (cough, sore throat, or nasal symptoms) of at least moderate severity.
5. Presence of at least one constitutional symptom (myalgia [aches and pains], headache, feverishness, or fatigue) of at least moderate severity.
6. Onset of symptoms no more than 48 hours before presentation for screening.
7. Written informed consent.

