#### 10.1.5 Vital Signs

Vital signs evaluations will include blood pressure, pulse rate, and respiration rate. The investigator will record oral or rectal body temperature at baseline. Thereafter the subject will

record oral temperature twice daily in the study diary card.

Vital signs will be measured at Screening/Baseline, pre-dose, and at 15 minutes following the study drug injection on Day 1, then once daily on Days 3, 5, 9, and 14.

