#### **10.1.11 Subject Self Assessments**

Subject self assessments will be performed beginning pre-dose on Day 1 and recorded in the subject's Study Diary including the following:

- Oral temperature measurements with an electronic thermometer (provided by the Sponsor for the study) every 12 hours. With the exception of the baseline measurement, all temperature measurements will be obtained at least 4 hours after, or immediately before, administration of oral acetaminophen (paracetamol, provided) or other anti-pyretic medications. The times of each temperature determination will be recorded in the Study Diary. The baseline temperature will be recorded at the screening/Day 1 visit prior to dosing, regardless of whether the subject had recently taken an anti-pyretic.
- Assessment of seven influenza symptoms (cough, sore throat, nasal obstruction, myalgia [aches and pains], headache, feverishness, and fatigue) on a 4-point severity scale (0, absent; 1, mild; 2, moderate; 3, severe) twice daily, beginning pre-dose on Day 1 and through Day 9, then once daily through Day 14.
- Assessment of the subject's time lost from work or usual activities and productivity compared to normal using a 0-10 visual analogue scale once daily through Day 14.

The subject's diary card will be reviewed by study staff at each visit for completion of the record of all required items, with particular emphasis on alleviation of symptoms as well as relapse of symptoms. Relapse is defined as the recurrence of at least one respiratory symptom and one constitutional symptom (both greater than mild in severity) for 24 hours and the presence of fever (unless influenced by antipyretic use). Relapse can only occur after the subject has met the endpoint criteria for alleviation of symptoms. Study staff will not attempt to ask subjects to retrospectively complete missing diary card data for any scheduled assessments that have not been completed prior to the clinic visit. Study staff should, however, remind the subject to complete the diary card at all scheduled times.

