Vital sign measurements (blood pressure, pulse rate, respiration rate, and oral temperature) and a 12 lead ECG will be obtained prior to dosing.

A nasopharyngeal swab for influenza culture/ PCR assay will be obtained prior to dosing.

### 10.3.2 Post-dose Evaluations-Study Day 1

The blinded study drug will be administered (hour 0) as bilateral intramuscular injections within a period of  $\leq 10$  minutes. The calendar date and 24-hour clock time of the first and second injections will be recorded. The gluteal site of injection and the syringe needle length are also to be recorded in the subjects CRF. Sites are instructed to follow procedures for intramuscular injection, with a recommended needle length appropriate to the physical characteristics of the subject, provided in the study drug administration manual.

The following evaluations will be performed post-dose on Study Day 1:

- Vital sign measurements (blood pressure, pulse rate, respiration rate, and oral temperature) 15 minutes following the second intramuscular injection of blinded study drug; record the exact 24-hour clock time of the vital sign measurements in the subjects CRF.
- Draw a PK sample between 30 and 60 minutes following the second intramuscular injection of blinded study drug; record the exact 24-hour clock time of the blood draw.
- Record any concomitant medications.
- Record any AEs.

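### Time to resolution of fever is compared without the pre-dose temperature scheduled in every subject; prespecifying it would be a cheap and probably modest gain in precision, not the repair of an error.

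*Combined protocol and SAP*

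**What the plan says.** All references are to protocol Version 4.0.

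- **Endpoint.** Section 6.2.2 lists two secondary clinical endpoints: time to resolution of fever and incidence of influenza-related complications. Oral temperature level is not listed.
- **Tests.** Section 12.7.2 says of oral temperature: "Differences between the 300 mg peramivir treatment group and placebo will be assessed using the van Elteren test controlling for smoking status", and the sentence goes on to add influenza A or B. For time to resolution it says: "Differences between the treatment groups will be assessed using the Wilcoxon-Gehan statistic controlling for smoking status", again with influenza type added. Resolution means a temperature below 37.2 °C with no antipyretic for at least 12 hours.
- **Covariates.** Section 12.10.2: "Primary and secondary efficacy analyses will be adjusted for smoking status and positive PCR or viral culture for influenza A or B at screening". Temperature is not mentioned.
- **Baseline reading.** Section 10.1.11: "The baseline temperature will be recorded at the screening/Day 1 visit prior to dosing, regardless of whether the subject had recently taken an anti-pyretic". Section 10.3.1 schedules an oral reading: "Vital sign measurements (blood pressure, pulse rate, respiration rate, and oral temperature) and a 12 lead ECG will be obtained prior to dosing". Section 10.1.5 is looser about the route: "The investigator will record oral or rectal body temperature at baseline".
- **Entry.** Section 8.1.1, criterion 3, requires at least 38.0 °C orally or 38.5 °C rectally, but also: "A subject self-report of a history of fever or feverishness within the 24 hours prior to screening will also qualify for enrollment".

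Viral titer, in the same section 12.7.2, is analysed as a change from baseline. Section 12.2 leaves further detail to a SAP whose text is not among the documents supplied.

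**The concern.** Criterion 3 lets starting temperature run from no measured fever to high fever. A subject at 39.5 °C has 2.3 °C to fall to reach the threshold; a subject at 38.0 °C has 0.8 °C; a subject already below 37.2 °C has nothing to resolve. If starting temperature predicts when fever ends, leaving it out puts that spread into the error term. The Gehan statistic gives most weight to early events, which is where subjects with little or no fever at entry would fall.

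The reading precedes treatment, so adjusting for it does not bias the comparison and does not change the endpoint. At stake is some precision on one of two secondary clinical endpoints, with no extra data to collect.

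**Working it through.** **1. The plan's own figure.** Section 12.4 claims at least 90% power for HR 0.70 with 450 influenza A subjects, 300 and 150, at two-sided alpha 0.05. Schoenfeld's formula gives (1.960 + 1.282)² / [(1/3)(2/3)(ln 0.70)²] = 372 events. With exponential medians of 137.0 h and 0.70 × 137.0 = 95.9 h, the fractions alleviated by 336 h are 81.7% and 91.2%, or 88.0% overall, hence 396 events. Power is 91.7% with 396 events and 94.6% if all 450 have the event. The claim reproduces, but it concerns the primary endpoint only. No power or precision figure is given for fever or temperature.

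**2. General size of the gain.** If baseline correlates with the outcome score at ρ, adjustment multiplies the variance by 1 − ρ². Effective N is 450 / (1 − ρ²), and a test with 80% power moves to Φ[(1.960 + 0.842)/√(1 − ρ²) − 1.960]. The values of ρ are assumed.

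| ρ | variance saved | effective N | power |
|---|---|---|---|
| 0.1 | 1% | 455 | 80.4% |
| 0.2 | 4% | 469 | 81.6% |
| 0.3 | 9% | 495 | 83.6% |
| 0.4 | 16% | 536 | 86.4% |
| 0.5 | 25% | 600 | 89.9% |

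**3. Check with Gehan tests.** 450 subjects at 2:1, censored and coarsely tied times, 800 runs per alternative, Monte Carlo standard error about 1.3 points. The baseline enters either as tertile strata or as the covariate in a Gehan-score rank ANCOVA.

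| ρ | unadjusted | tertile strata | rank ANCOVA |
|---|---|---|---|
| 0 | 83.0% | 81.6% | 82.5% |
| 0.2 | 82.8% | 83.6% | 84.0% |
| 0.3 | 80.5% | 83.6% | 82.9% |
| 0.5 | 82.9% | 89.1% | 91.3% |

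Type I error stayed between 3.3% and 6.3% (600 runs each).

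**4. Time to resolution with the 38.0 °C stratum.** The size is 600 × 313/344 ≈ 546 infected subjects (364 and 182), using the phase 2 infection rate; influenza B is 66/313 = 21%. Assumed: 25% smokers, baseline B normal with mean 38.4 °C and SD 0.6 °C, decay 37 + (B − 37)exp(−kt), 12-hourly readings, 2,500 runs.

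| SD of log k | baseline share of variance of log time | 4 strata | 8 strata | gain |
|---|---|---|---|---|
| 0.5 | 0.26 | 79.5% | 85.7% | 6.2 |
| 0.8 | 0.14 | 76.4% | 80.1% | 3.7 |
| 1.0 | 0.09 | 76.4% | 77.4% | 1.0 |

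A separate run of the same model (1,000 runs) gave gains of 5.6, 3.1 and 2.5 points. With half of the baselines lowered by 0.8 °C through antipyretics (assumed), they were 2.0, 1.4 and 2.3. The 12-hour antipyretic rule is not modelled.

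**5. Oral temperature by visit.** With the same 364 and 182 and an assumed shift of 0.26 SD, rank ANCOVA against the plain Wilcoxon test gave 78% to 82% (correlation 0.3), 79% to 86% (0.4) and 79% to 89% (0.5).

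**6. Cell sizes and subjects with no fever, on the step 4 assumptions.** Influenza B smokers: 546 × 0.25 × 0.21 ≈ 29. The share below 38.0 °C is Φ[(38.0 − 38.4)/0.6] = 25%, so the smallest of the eight cells holds about 7 subjects. The share below 37.2 °C is Φ(−2) = 2.3%, about 12 subjects. If half the readings are 0.8 °C lower, it is 0.5 × 2.3% + 0.5 × 25% ≈ 14%, about 75 subjects.

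**The case against.** The strongest reply is that nothing here is wrong. Both tests are valid under randomisation without baseline adjustment, chance imbalance is already covered by the type I error, and the planned strata follow the randomisation factors (smoking, and influenza type by RAT at randomisation but by PCR or culture in the analysis). That stands, and it makes this an optional improvement.

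The size is also open to attack. Every correlation is assumed, and the decay model builds in prognostic value by making time to 37.2 °C depend directly on the baseline. Antipyretics blunt the reading before dosing and enter the endpoint through the 12-hour rule. These points stand and pull the likely gain towards the lower end.

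A reader might infer from step 5 that a secondary endpoint forgoes up to 10 points of power. The documents do not support this: step 5 concerns oral temperature by visit, which section 6.2.2 does not list. Nor is the adjustment free, given eight strata in place of four.

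Finally, the matter may be handled elsewhere. The synopsis says other continuous endpoints are treated like changes in viral titer, and a SAP is to follow. But the synopsis sentence does not put baseline temperature into either test, and section 12.10.2 leaves it out. The point can be made only about the protocol text. A plain change score would not be a safe answer either: its variance factor is 2 − 2ρ, worse than no adjustment when ρ is below 0.5.

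**Conclusion.** The omission is real in Version 4.0: both fever comparisons, and the general covariate list, leave out a pre-dose reading scheduled for every subject. It costs precision, not validity. For time to resolution the gain from adjusting is about 1 to 6 points of power under the assumed decay model and about 1 to 2 points when half the baselines are masked. If baseline carries no information, about 0 to 1 point is lost. The documents supply no correlation, temperature SD or fever duration, so no single figure can be defended.

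It would go too far to infer that the fever results would be biased or the trial underpowered. Treatment is randomised, the tests keep their level, and section 12.4 sizes the trial on the primary endpoint alone. A separate gap is worth closing at the same time: nothing says how a subject already below 37.2 °C before dosing enters the time-to-resolution analysis, and the 38.0 °C cut does not settle it. This is a low-priority, worthwhile edit.

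**What to change.** In sections 12.7.2 and 12.10.2, before unblinding:

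1. **Time to resolution of fever.** Add pre-dose oral temperature, below 38.0 °C against 38.0 °C or above (the oral cut already in criterion 3), as a third stratum in the Wilcoxon-Gehan test. If the eight cells are too sparse, use it instead as the covariate in a Gehan-score rank ANCOVA, with the rule for choosing fixed in advance.
2. **Oral temperature by visit.** Replace the plain van Elteren test with a stratified rank ANCOVA using the same baseline and the existing strata.
3. **Which reading.** Name the pre-dose oral measurement in section 10.3.1, because section 10.1.5 allows a rectal one.
4. **No fever at entry.** State how subjects already below 37.2 °C before dosing enter the time-to-resolution analysis, including those who had recently taken an antipyretic.

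The cost is some protocol or SAP wording and a few program lines, with no new data. The downside is more strata, with little information in the smallest cells (influenza B smokers).
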